3.2 Endpoints

The primary endpoints are:

- The incidence of DLTs in Cohort 1
- The MTD, or in the absence of an MTD the RP2D, of tabelecleucel when administered in combination with pembrolizumab
- The ORR of tabelecleucel in combination with pembrolizumab
- The characterization of the safety profile of tabelecleucel in combination with pembrolizumab in subjects with NPC

Secondary endpoints are:

- CR rate, DOR, PFS, and OS
- iRR (ie, iCR + iPR rate) and DOiR

Exploratory endpoints are:

CCI

CCI

3.3 Study Stopping Criteria

This study includes the following design elements to reduce risk to subjects:

- Dose de-escalation based on the number of DLTs experienced; DLTs are described in Section 5.2.3
- Cohort review: all Cohort 1 data will be reviewed by the SDRC prior to beginning enrollment of Cohort 2
- DLT review: when a DLT is reported, the event is reviewed within the context of all treated subjects and available study data

The sponsor may suspend treatment and/or enrollment to assess risk based on any of the following:

- Number of DLTs experienced as described in Section 5.2.3
- Identification of a significant safety signal that requires time for further assessment

Depending on the outcome of these reviews, the sponsor may amend the protocol or stop the study.

3.4 Safety Data Review Committee

A SDRC composed of representatives from the sponsor and the principal investigators or designated sub-investigators from all sites enrolling subjects in Cohort 1 will review reported DLTs and cumulative safety data to determine further enrollment. The data review will occur as soon as possible after Cycle 1 Day 21 of the last subject in Cohort 1.

The sponsor's medical monitor and global safety officer will review data on an ongoing basis and may suspend dosing and/or enrollment and convene a SDRC meeting at any time based on emerging safety data.

3.5 Dose and Dose De-escalation Plans

The study dose and dose de-escalation plans, which will include applicable review(s) by the SDRC (Section 3.4), is described as follows:

- At the 2×10^6 dose level:
 - If ≤ 1 of the first 6 subjects in Cohort 1 experiences DLTs, the next 6 subjects will be enrolled in Cohort 1 at the 2×10^6 dose level.
 - If ≤ 3 of the 12 total subjects in Cohort 1 experience DLTs, Cohort 2 will proceed with enrollment of 36 subjects at the 2×10^6 dose level.
 - If ≥ 2 of the first 6 subjects experience DLTs, the dose will be de-escalated to 1×10^6 , and the next 6 subjects will be enrolled in Cohort 1 at the lower dose level of 1×10^6 . Continue with the steps for the 1×10^6 dose level.
 - If ≥ 4 of the 12 total subjects experience DLTs, the dose will be de-escalated to 1×10^6 and the next 6 subjects will be enrolled in Cohort 1 at the lower dose level of 1×10^6 . Continue with the steps for the 1×10^6 dose level.
- At the 1×10^6 dose level:
 - If ≤ 1 of the first 6 subjects experiences DLTs, the next 6 subjects will be enrolled in Cohort 1 at the 1×10^6 dose level.
 - If ≤ 3 of the 12 total subjects in Cohort 1 experience DLTs, Cohort 2 will proceed with enrollment of 36 subjects at the 1×10^6 dose level.
 - If ≥ 2 of the first 6 subjects or > 4 of the 12 total subjects experience DLTs, all further enrollment will be stopped and continued dosing of current subjects receiving active treatment will be evaluated by SDRC for an individual benefit-risk assessment.

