3 INVESTIGATIONAL PLAN

3.1 Study Design

This is a multicenter, open-label, single-arm study in subjects with platinum-pretreated, recurrent/metastatic EBV+ NPC (also referred to as NPC in this protocol). The study will be conducted in 2 parts: Cohort 1 will be enrolled as the phase 1B portion to determine the phase 2 dose; Cohort 2 will be enrolled as the phase 2 portion to examine the clinical benefits of combined T cell and checkpoint inhibitor immunotherapies for the treatment of subjects with NPC. The study will enroll 48 to 60 subjects in total. Phase 1B (Cohort 1) will enroll 12 to 24 subjects. For each dose level explored in Cohort 1, at least 6 subjects must have had disease that is refractory to PD-1 or PD-L1 monoclonal antibody. All other subjects enrolled to Cohort 1 will be checkpoint inhibitor naïve subjects (have never received pembrolizumab or other anti-PD-1, anti-PD-L1, anti-PD-L2, anti-CD137, anti-OX40 [CD134] or anti-CTLA-4 products). Dose de-escalation is permitted in Cohort 1 only. Cohort 2 will enroll 36 subjects who are checkpoint inhibitor naïve.

Tabelecleucel will be selected for each subject from the bank of available tabelecleucel cell products based on matching ≥ 2 HLA alleles, at least one of which is a restricting HLA allele, ie, shared between the tabelecleucel source material (donor) and the subject.

The overall treatment schema is shown in [Figure 1](#) and the planned dose cohorts are provided in [Table 2](#). In Cohort 1, tabelecleucel will be administered initially to 12 subjects at a dose of 2×10^6 cells/kg IV on Day 1, Day 8, and Day 15 of a 21-day cycle. Pembrolizumab will be administered to adult subjects (≥ 18 years of age) at a dose of 200 mg IV Q3W (ie, on Day 1 of each 21-day cycle) and to pediatric (adolescent) subjects (12 to < 18 years of age) at a dose of 2 mg/kg IV Q3W. If ≥ 2 of the initial 6, or ≥ 4 of the initial 12, Cohort 1 subjects experience a DLT in the first 21 days, the dose of tabelecleucel will be reduced to 1×10^6 cells/kg/dose, and an additional 12 subjects will be treated with the combination of tabelecleucel at 1×10^6 cells/kg/dose and pembrolizumab at the recommended dose level ([Table 3](#)). Otherwise,

all 12 subjects in Cohort 1 will receive tabelecleucel at 2×10^6 cells/kg/dose and pembrolizumab at the recommended dose level.

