 - Grade 4 thrombocytopenia of any duration
 - Grade 3 thrombocytopenia associated with bleeding that requires a platelet transfusion
- Any nonhematologic AE grade ≥ 3 in severity should be considered a DLT, with the following exceptions: grade 3 fatigue lasting ≤ 3 days; grade 3 diarrhea, nausea, or vomiting without use of anti-emetics or anti-diarrheals per standard of care; grade 3 rash without use of corticosteroids or anti-inflammatory agents per standard of care.
- Any grade 3 or grade 4 non-hematologic laboratory value if:
 - Clinically significant medical intervention is required to treat the subject, or
 - The abnormality leads to hospitalization, or
 - The abnormality persists for > 1 week.
 - The abnormality results in a Drug-induced Liver Injury (DILI)
 - Exceptions: Clinically nonsignificant, treatable, or reversible laboratory abnormalities including liver function tests, uric acid, etc.

- Febrile neutropenia grade 3 or grade 4:
 - Grade 3 is defined as ANC < 1000/mm³ with a single temperature of > 38.3 degrees C (101 degrees F) or a sustained temperature of ≥ 38 degrees C (100.4 degrees F) for more than 1 hour
 - Grade 4 is defined as ANC < 1000/mm³ with a single temperature of > 38.3 degrees C (101 degrees F) or a sustained temperature of ≥ 38 degrees C (100.4 degrees F) for more than 1 hour, with life-threatening consequences and urgent intervention indicated.
- Prolonged delay (> 2 weeks) in initiating Cycle 2 due to treatment-related toxicity.
- Any treatment-related toxicity that causes the subject to discontinue treatment during Cycle 1.
- Missing > 25% of pembrolizumab or tabelecleucel doses as a result of investigational product-related AE(s) during the first cycle.
- Grade 5 toxicity.

Any subject experiencing any DLT will be withdrawn from treatment (both investigational products). Whenever possible, protocol-defined follow-up will be continued after the subject has discontinued investigational product treatment (refer to Section 6.7).

MTD definition: The MTD is defined as the highest dose level at which the subject incidence of a DLTs during the first 21-day cycle of investigational product dosing is < 33%.

RP2D definition: The RP2D is no higher than the MTD and is based on optimal benefit-risk, as determined by the SDRC.

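### At the 1×10^6 dose level, exactly 4 DLTs in 12 subjects has no assigned action; the stop should be at 4 or more, not more than 4

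*Protocol*

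**What the plan says.** Protocol section 3.5 sets out a 6+6 scheme at each dose level.

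- **2×10^6, 12 subjects.** Cohort 2 opens at 3 or fewer DLTs. Otherwise: "If ≥ 4 of the 12 total subjects experience DLTs, the dose will be de-escalated". These two rules cover every total.
- **1×10^6, first 6 subjects.** With 0 or 1 DLT, six more are enrolled. With 2 or more, enrollment stops.
- **1×10^6, 12 subjects.** At 3 or fewer DLTs, "Cohort 2 will proceed with enrollment of 36 subjects at the 1×10^6 dose level". The stop is written as "> 4 of the 12 total subjects experience DLTs, all further enrollment will be stopped", and the same bullet adds that "continued dosing of current subjects receiving active treatment will be evaluated by SDRC for an individual benefit-risk assessment".

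Section 5.2.3 defines the MTD as the highest dose level at which the subject incidence of "DLTs during the first 21-day cycle of investigational product dosing is < 33" percent, and caps the RP2D at the MTD. The synopsis, sections 3.1 and 5.2.5.4, and SAP section 2.2 repeat only the de-escalation rule from 2×10^6. None of them gives a separate stop for 1×10^6.

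**The concern.** The two 12-subject rules at 1×10^6 do not meet. Proceeding ends at 3 and stopping begins at 5, so a total of 4 has no stated action. This is the lowest planned dose, and 4/12 means that it has failed the protocol's own tolerability criterion.

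Two things are left unwritten at that outcome: a mandatory stop to enrollment, and the SDRC's individual evaluation of whether current subjects should go on being dosed. That evaluation appears only in the stop bullet. The committee's routine task in section 3.4 is that it "will review reported DLTs and cumulative safety data to determine further enrollment", and the power given there to the medical monitor and global safety officer is optional: they "may suspend dosing and/or enrollment and convene a SDRC meeting at any time".

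**Working it through.** **Inputs.** From section 3.5: proceed at ≤ 3/12; stop at ≥ 2/6 or > 4/12 (1×10^6); de-escalate at ≥ 2/6 or ≥ 4/12 (2×10^6). From section 5.2.3: the MTD needs an incidence below 33%. The documents state no expected DLT rate p, so p = 10%, 15%, 20%, 25%, 33% and 40% are assumed.

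**Where the boundary belongs.** 3/12 = 25.0% meets the MTD criterion. 4/12 = 33.3% does not. The 12-subject stop should therefore begin at 4, as the corresponding rule does at 2×10^6. As written it begins at 5/12 = 41.7%.

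**How often 4/12 arises once 1×10^6 opens.** Let A ~ Bin(6, p) be the DLTs in the first six (continue if A ≤ 1), B ~ Bin(6, p) those in the next six, and T = A + B. Then

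P(T = 4) = P(A=0)·P(B=4) + P(A=1)·P(B=3).

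At p = 0.20: 0.2621 × 0.0154 + 0.3932 × 0.0819 = 0.0040 + 0.0322 = 0.0362.

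The other quantities are P(proceed) = P(A ≤ 1, T ≤ 3); P(stop as written) = P(A ≥ 2) + P(A ≤ 1, T ≥ 5); and P(stop with ≥ 4) = P(A ≥ 2) + P(A ≤ 1, T ≥ 4).

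| Assumed p | Exactly 4/12 | Proceed (either wording) | Stop, as written | Stop, with ≥ 4 |
|---|---|---|---|---|
| 10% | 0.6% | 87.9% | 11.5% | 12.1% |
| 15% | 1.9% | 75.5% | 22.6% | 24.5% |
| 20% | 3.6% | 61.2% | 35.2% | 38.8% |
| 25% | 5.3% | 46.7% | 48.0% | 53.3% |
| 33% | 6.5% | 26.5% | 67.0% | 73.5% |
| 40% | 5.8% | 14.0% | 80.2% | 86.0% |

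With ≥ 4, proceed and stop sum to 100% in every row. As written, they fall short by exactly P(T = 4).

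**Share of failures without a written stop.** P(T = 4) / (1 − P(proceed)) runs from 0.0058/0.1206 = 4.8% (p = 10%) to 0.0528/0.5331 = 9.9% (p = 25%). The first-six rule catches most of the rest. Among paths that reach 12 subjects and then fail, exactly 4/12 is the commonest result: at p = 20%, 0.0362/(0.0362 + 0.0071) = 84%.

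**Who the missing evaluation concerns.** Section 5.2.3 withdraws every subject with a DLT. That leaves at most 12 − 4 = 8 subjects at 1×10^6. To these add at most 6 − 2 = 4 still on treatment from 2×10^6 (if de-escalation followed ≥ 2/6) or 12 − 4 = 8 (if it followed ≥ 4/12).

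**The case against.** The strongest reply is that nothing turns on the symbol, and much of that is right.

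- **Cohort 2 cannot open at 4/12.** The proceed condition is unmet, the level's size is used up (section 3.1: "an additional 12 subjects will be treated with the combination of tabelecleucel"), and 1×10^6 qualifies as neither MTD nor RP2D. This stands, so no extra Cohort 2 exposure is claimed.
- **Other safeguards exist.** SDRC review before Cohort 2 is mandatory. Section 3.3 requires each reported DLT to be reviewed against all treated subjects and lets the sponsor suspend treatment on the number of DLTs. These narrow the gap without closing it: the per-event review names neither the SDRC nor a subject-by-subject decision on continuing, and suspension is discretionary.
- **The 2×10^6 rules also omit an individual evaluation.** True, and it weakens the safety argument. But the protocol does prescribe that evaluation when the lowest dose fails, and then misses one of the failing totals.
- **The table is conditional on 1×10^6 opening.** Correct. If both levels share the same DLT rate, the chance of opening equals the last column, because the 2×10^6 rule is the same as the corrected one. Multiplying by the second column gives trial-level chances of about 0.07%, 0.5%, 1.4%, 2.8%, 4.8% and 5.0%.
- **It is moot.** SAP section 1 reports termination at Phase 1B with 12 enrolled. Twelve subjects at 1×10^6 would need at least 6 + 12 = 18. No SAP analysis uses the rule.
- **The symbol might have been misread from the PDF.** This cannot be excluded without the PDF, but the ≥ sign before 2 reads correctly in the same bullet.

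**Conclusion.** The concern holds. Section 3.5 assigns no action to 4/12 at 1×10^6, and both the MTD definition and the parallel 2×10^6 rule put the boundary at 4 or more. Under assumed DLT rates of 10% to 40%, the same for every subject and independent between subjects, the uncovered outcome has a chance of 0.6% to 6.5% once the level opens, and roughly 0.07% to 5.0% over the whole trial if both levels share one rate. It is a certain but minor defect in a safety rule. It changes neither the probability of opening Cohort 2 nor any planned analysis, and it could not have affected the study as conducted.

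**What to change.** In the last 1×10^6 bullet of section 3.5, replace > 4 with ≥ 4 for the 12-subject total. Every total then has an action: 3 or fewer proceeds; 4 or more stops enrollment and triggers the SDRC evaluation of current subjects. No other section needs to change. The cost is one character, with no added patients, procedures or time.

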4 SELECTION AND WITHDRAWAL OF SUBJECTS

4.1 Number of Subjects

Up to a total of 48 to 60 subjects will be enrolled in the study. The phase 1B portion (Cohort 1) of the study will enroll 12 to 24 subjects. For each dose level explored in Cohort 1, at least 6 subjects must have disease that is refractory to a PD-1 or PD-L1 monoclonal antibody. The other subjects enrolled to Cohort 1 will be checkpoint inhibitor naïve subjects (have never received pembrolizumab or any other anti-PD-1, anti-PD-L1, anti-PD-L2, anti-CD137, anti-OX40 or anti-CTLA-4 antibodies). The phase 2 portion (Cohort 2) of the study will enroll 36 subjects who are checkpoint inhibitor naïve.

4.2 Eligibility Criteria

Subjects must undergo a tablecleucel inventory check to ensure availability of an appropriately matched and restricted tablecleucel cell product prior to undergoing screening procedures. The inventory check includes collection of the subject's high-resolution HLA typing (DNA-based versus serologic assessment) and weight.

Investigators may submit de-identified information (ie, historically available high-resolution HLA typing and current weight) for potential subjects being referred from outside institutions (as long as the referring physician has documented in the potential subject's chart that s/he was notified that their data was being sent through a study investigator to Atara Biotherapeutics, Inc. and that the potential subject consented for this to be done). This de-identified information will be used to determine whether an appropriately HLA-matched product is available to warrant a referral to the study site for potential study participation.

4.2.1 Inclusion Criteria

A subject will be considered eligible to participate in this study if all of the following inclusion criteria are satisfied:

1. Male or female \geq 12 years of age
2. Incurable, locally recurrent or metastatic NPC (World Health Organization type II/III) in whom the EBV nucleic acid or antigens have been demonstrated in tissue biopsy samples
3. Subjects must have had prior receipt of platinum-containing regimen, *either*:
 - a. For the treatment of recurrent or metastatic disease, *or*
 - b. Experienced progression of disease within 6 months following completion of a platinum-based combination therapy as part of (neo)adjuvant chemotherapy. Note: Patients who had only concurrent chemoradiation therapy without (neo)adjuvant therapy and then recurred/metastasized must have progressed on at least 1 platinum-containing regimen for their recurrent/metastatic disease before study entry.
4. Phase 1B (Cohort 1):
 - a. Checkpoint inhibitor naïve (have never received pembrolizumab or any other anti-PD-1, anti-PD-L1, anti-PD-L2, anti-CD137, anti-OX40 or anti-CTLA-4 antibodies)

OR

- b. Refractory to an anti-PD-1 or anti-PD-L1 monoclonal antibody approved by the local regulatory agency either as monotherapy or in combination with other checkpoint inhibitors or therapies according to their approved label. To be considered refractory to an anti-PD-1 or anti-PD-L1 monoclonal antibody, all of the following criteria must be met:
 - i. Received at least 2 doses of anti-PD-1 or anti-PD-L1 monoclonal antibody at a local regulatory agency-approved dose and schedule.

- ii. Have progressive disease after anti-PD-1 or anti-PD-L1 monoclonal antibody as defined according to RECIST 1.1. The initial evidence of progressive disease is to be confirmed by a second assessment, no less than 4 weeks from the date of the first documented progressive disease, in the absence of rapid clinical progression. (The eligibility determination will be made by the investigator and then the sponsor will collect for retrospective analysis at a central vendor. Once progressive disease is confirmed, the initial date of progressive disease documentation will be considered the date of disease progression).
- iii. Documented disease progression within 24 weeks of the last dose of anti-PD-1 or anti-PD-L1 monoclonal antibody. A subject who was re-treated with anti-PD-1 or anti-PD-L1 monoclonal antibody and a subject who was on maintenance with an anti-PD-1 or anti-PD-L1 monoclonal antibody will be allowed to enter the study as long as there is documented PD within 24 weeks of the last treatment date (with the anti-PD-1 or anti-PD-L1 monoclonal antibody).

5. Phase 1B (Cohort 1): If PD-1/PD-L1 failure (ie, refractory to or relapsed after PD-1/PD-L1 treatment), must have a lesion that can be biopsied after administration of tabelecleucel with acceptable clinical risk (as judged by the investigator) and must agree to undergo biopsy before Cycle 1 Day 1
6. Phase 2 (Cohort 2): Checkpoint inhibitor naïve (have never received pembrolizumab or any other anti-PD-1, anti-PD-L1, anti-PD-L2, anti-CD137, anti-OX40 or anti-CTLA-4 antibodies)

CCI

8. Life expectancy \geq 4 months at time of screening
9. Measurable disease using RECIST 1.1. Tumor lesions situated in a previously irradiated area are considered measurable if progression has been documented in such lesions.
10. Eastern Cooperative Oncology Group (ECOG) performance status of < 2 for subjects aged > 16 years; Lansky score \geq 70 for subjects aged 12 to 16 years (refer to Section 15.2)
11. Adequate organ function per the following:

System	Laboratory Value
Hematological	
ANC	\geq 1,500/ μ L
Platelets	\geq 100,000/ μ L
Hemoglobin ^a	\geq 9 g/dL or \geq 5.6 mmol/L
Renal	
Creatinine OR Measured or calculated creatinine clearance ^b (GFR can also be used in place of creatinine or CrCl)	\leq 1.5 x ULN OR \geq 30 mL/min for subject with creatinine levels $>$ 1.5 x ULN

System	Laboratory Value
Hepatic	
TBILI	$\leq 1.5 \times \text{ULN}$ OR Direct bilirubin $\leq \text{ULN}$ for subjects with TBILI $> 1.5 \times \text{ULN}$
AST (SGOT) and ALT (SGPT)	$\leq 2.5 \times \text{ULN}$ $\leq 5 \times \text{ULN}$ for subjects with liver metastases
Coagulation	
INR or PT aPTT	$\leq 1.5 \times \text{ULN}$ unless subject is receiving anticoagulant therapy as long as PT or aPTT is within therapeutic range of intended use of anticoagulants

ANC: absolute neutrophil count; aPTT: activated partial thromboplastin time; ALT (SGPT): alanine aminotransferase (serum glutamic pyruvic transaminase), AST (SGOT): aspartate aminotransferase (serum glutamic oxaloacetic transaminase), GFR: glomerular filtration rate, INR: international normalized ratio; PT: prothrombin time; TBILI: total bilirubin; ULN: upper limit of normal.

^a Criteria must be met without erythropoietin dependency and without packed red blood cell (pRBC) transfusion within last 2 weeks.

^b Creatinine clearance should be calculated per institutional standard.

12. Willing and able to provide written informed consent (pediatric subjects 12 to < 18 years of age must provide assent along with consent from the subject's legally authorized representative)

4.2.2 Exclusion Criteria

A subject will not be eligible to participate in the study if any of the following criteria are met:

1. Disease that is suitable for local therapy administered with curative intent
2. Receives vasopressor or ventilator support
3. Received antithymocyte globulin or similar anti-T cell antibody therapy ≤ 4 weeks prior to Cycle 1 Day 1
4. Diagnosis of immunodeficiency or is receiving systemic steroid therapy or any other form of immunosuppressive therapy within 7 days prior to Cycle 1 Day 1 of study treatment. The use of physiologic doses of corticosteroids may be approved after consultation with the sponsor's medical monitor.
5. Active autoimmune disease that has required systemic treatment in past 2 years (ie, with use of disease modifying agents, corticosteroids or immunosuppressive drugs). Replacement therapy (eg, thyroxine, insulin, or physiologic corticosteroid replacement therapy for adrenal or pituitary insufficiency) is not considered a form of systemic treatment and is allowed.
6. History or evidence of interstitial lung disease
7. History of severe hypersensitivity (Grade ≥ 3) to pembrolizumab and/or any of its excipients
8. Active infection requiring systemic therapy

9. History of (non-infectious) pneumonitis that required steroids or current pneumonitis
10. Received transfusion of blood products (including platelets or red blood cells) or administration of colony stimulating factors (including granulocyte-colony stimulating factor, granulocyte macrophage-colony stimulating factor or recombinant erythropoietin) within 4 weeks prior to study Day 1
11. Unresolved immunotherapy-related AEs or treatment for these events within 4 weeks prior to enrollment
12. History of severe immunotherapy-related adverse effects (Common Terminology Criteria for Adverse Events [CTCAE] grade 4 or CTCAE grade 3 requiring treatment > 4 weeks)
13. Received any non-oncology vaccine therapy used for prevention of infectious diseases for up to 30 days prior to enrollment. Examples include, but are not limited to: measures, mumps, rubella, chicken pox, yellow fever, rabies, bacille Calmette-Guerin, and typhoid vaccine. Seasonal flu vaccines that do not contain live virus are acceptable.
14. Known additional malignancy that is progressing or requires active treatment. Exceptions include basal cell carcinoma of the skin, squamous cell carcinoma of the skin that has undergone potentially curative therapy or in situ cervical cancer.
15. Pregnancy or breastfeeding; females of childbearing potential must have a negative serum pregnancy test. The serum pregnancy must be confirmed negative within 72 hours of Cycle 1 Day 1 (first dose of investigational product) for the subject to be eligible.
16. Female of childbearing potential or male with a female partner of childbearing potential unwilling to use a highly effective method of contraception (abstinence is acceptable) for the course of the study through 120 days after the last study dose.
17. Inability to comply with study procedures
18. Received chemotherapy or targeted small molecule therapy within 2 weeks of Cycle 1 Day 1. Subjects must have recovered (ie, grade ≤ 1 or at baseline) from AEs due to a previously administered agent. Subjects with grade ≤ 2 neuropathy or grade ≤ 2 alopecia are an exception to this criterion.
19. Received prior radiotherapy within 2 weeks of Cycle 1 Day 1. Subjects must have recovered from all radiation-related toxicities, not require corticosteroids, and not have had radiation pneumonitis. A 1-week washout is permitted for palliative radiation (≤ 2 weeks of radiotherapy) to non-central nervous system (CNS) disease.
20. Antibody/biologic therapy within 4 weeks of Cycle 1 Day 1 or not recovered (ie, grade ≤ 1 or at baseline) from AEs due to agents administered more than 4 weeks earlier
21. Carcinomatous meningitis and/or active CNS metastases, unless metastases are treated and stable and the subject does not require systemic steroids NOTE: Subjects with previously treated brain metastases may participate provided they are stable (without evidence of progression by imaging [using the identical imaging modality for each assessment, either magnetic resonance imaging (MRI) or computed tomography (CT) scan] for at least four weeks prior to the first dose of investigational product and any neurologic symptoms have returned to baseline), have no evidence of new or enlarging

brain metastases, and are not using steroids for at least 7 days prior to first dose of investigational product. This exception does not include carcinomatous meningitis which is excluded regardless of clinical stability.

22. History or current evidence of any condition, therapy, or laboratory abnormality that might confound the results of the study, interfere with the subject's participation for the full duration of the study, or is not in the best interest of the subject to participate, in the opinion of the treating investigator
23. Known psychiatric or substance abuse disorders that would interfere with cooperation with the requirements of the study
24. Known history of human immunodeficiency virus (HIV), known active hepatitis B virus (HBV; eg, hepatitis B surface antigen [HBsAg] reactive), or hepatitis C virus (HCV; eg, HCV ribonucleic acid [RNA] is detected)
25. Prior treatment with any investigational product within 4 weeks of Cycle 1 Day 1
26. Prior treatment with EBV T cells

